Post-intensive care syndrome (PICS) is a common consequence of an intensive care unit (ICU) stay and can last up to 5 years.[1–3] The family members are often affected, reporting diminished quality of life and mental health related quality of life.[4] About 80% of family members become informal carers and 33% of families

see a significant reduction of income the first 6 months after discharge.[5] The extent to which these problems will be modified by the pandemic and coronavirus disease 2019 (COVID-19) remains unknown.

If under normal circumstances, an ICU stay has detrimental effects, the pandemic added two extra factors. Firstly, a rapid and exponential increase in acute care bed capacity might have affected the quality of care delivered by spreading too thin highly skilled healthcare staff. Secondly, COVID-19 involves a new disease with great uncertainties regarding treatment, prognosis and long-term effects. Early reports suggest that 64% of patients who were discharged from ICU after severe COVID-19 have at least one symptom of PICS at 6 months after discharge[6] and 32% had anxiety or depression symptoms,[7] which suggests these patients will have similar impairments to what has been reported for other ICU survivors previously.[8,9] Additionally, infection control protocols meant that healthcare staff had to wear personal protective equipment and family visiting was restricted.[10] These factors add another layer of potential negative effects due to challenges in communication with patients and their family members. Therefore, we hypothesize that the prevalence and severity of mental, physical, and cognitive impairments will be higher in patients treated in periods of higher bed occupancy and those who had severe COVID-19. In the case of family members, we expect that the experience of having a next of kin in the ICU during pandemic would be stressful and traumatic, but those with social support will cope better. In the case of staff members, their experiences will vary greatly depending on their profession and workplace, but we expect places with a more open/ less hierarchical structure to have coped better with the increase in demand.

The primary objective of this study is to compare the trajectory of mental, physical and cognitive impairments at ICU discharge, 3 and 6 months of mechanically ventilated adult patients who survived an ICU stay due to severe COVID-19 or other causes, during the pandemic. Secondary objectives are:

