- To compare the disability, quality of life and survival rate at ICU discharge, 3 and 6 months of patients who were admitted to ICU due to severe COVID-19 or other causes during high and low bed occupancy in the pandemic;
- To describe the sedentary behaviour and physical activity levels in a sample of ICU survivors during the COVID-19 pandemic using a one-week actigraphy protocol;
- To explore the psychological and emotional experiences reported by family members/next of kin of patients admitted to the ICU during the COVID-19 pandemic;
- To explore the emotional, intellectual, physical and administrative challenges faced by the participating ICU staff during the COVID-19 pandemic;
- To evaluate the feasibility of the follow-up from ICU discharge to 3 and 6 months during the pandemic.

METHODS

Study design and setting

The “Impact on Mental, Physical, And, Cognitive functioning of Critical care Time due to COVID-19” (IMPACCT-COVID19) is a prospective, multicentre, cohort study in seven Chilean academic medical-surgical ICUs. This study also involves a

qualitative component including semi-structured interviews with family members/next of kin of ICU survivors and with ICU staff from the participating centres. Participating sites are four public and three private hospitals comprising a pooled bed capacity of about 200 ICU beds for both COVID-19 patients and patients admitted for other causes. The IMPACCT-COVID19 study started in October 2020. Data collection is planned until November 2021 to achieve completion of the study in February 2022.

Study population and eligibility criteria

Adult patients (≥ 18 years old) who are mechanically ventilated for at least 48 hours in one of the participating ICUs and do not meet any of the exclusion criteria (**Table 1**) will be invited to participate.

Table 1. Exclusion and stopping follow-up criteria

Exclusion criteria	Rationale
Unable to walk independently 2 weeks prior to ICU admission (with or without a gait aid)	Potential confounding factor
S5q < 5 or CAM-ICU positive within 72 hours after ICU discharge	Unable to evaluate
Patient who do not understand or speak Spanish	Unable to evaluate
Patient unable to communicate verbally	Incomplete assessment data
Burn or severe trauma as admission diagnosis	Incomplete assessment data
Any neurological disorder (i.e. spinal cord injury, stroke and brain tumours) as admission diagnosis	Potential confounding factor

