The primary outcome measure is disability assessed at 6 months after ICU discharge using the World Health Organization Disability Assessment Schedule 2.0 (WHODAS 2.0) which is recommended for critical illness survivors.[8] The WHODAS 2.0 is a self-reported disability questionnaire based on the International Classification of Functioning, Disability, and Health (ICF). It includes 36 questions, organised under six domains (cognition, mobility, self-care, getting along, life activities and participation). Each question must be answered based on the perceived difficulty for performing activities using a 5-point scale (none, mild, moderate, severe and extreme).[15] We will use the Spanish version freely

available at <https://apps.who.int/iris/handle/10665/170500>.[16] The estimated response time ranges from 5 to 10 minutes when evaluated in-person at ICU discharge and 10 to 20 minutes when evaluated by telephone at 3 and 6 months after ICU discharge.

Secondary outcomes measures

Clinical Frailty Scale

The Clinical Frailty Scale (CFS) is a clinical judgment based tool developed for the Canadian Study of Health and Aging to evaluate the degree of frailty in elderly patients.[17] Currently, it is also used for critically ill patients.[18] The CFS evaluates specific domains including physical functioning, activities of daily living (ADL), instrumental ADL, assistance for personal care, comorbidities, and cognition to generate a frailty score using a 9-point scale ranging from 1 (very fit) to 9 (terminally ill). A score greater than 4 is considered fragile.[17] We will use the Spanish version and recommended training material by the developers at the Dalhousie University.[17,19] The estimated scoring time ranges from 1 to 5 minutes evaluated in-person at ICU discharge considering the status 2 weeks before the onset of symptoms.

Medical Research Council Sum Score (MRC-SS)

Limb muscle strength will be assessed using the MRC-SS, which consists in a standardised examination of six muscle groups bilaterally (i.e. shoulder abduction, elbow flexion, wrist extension, hip flexion, knee extension and dorsiflexion).[20] All muscle groups are scored using a 6-point scale between 0 and 5 (0 = no visible /

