the rest areas to capture a wider population. We will recruit medics, nurses, healthcare assistants and physiotherapists that normally work in an ICU and have patient-facing clinical duties for more than 96 hours during the pandemic. The invitation to participate will lead to a google form containing information about the study and a short script that constitutes the informed consent. From the list of volunteers, we will purposely sample three professionals per clinical group aiming to maximise variation regarding years of experience and centre where they work. We expect a minimum of 40 interviews, but we will continue recruitment until data saturation is achieved. Interviews will be conducted online or over the phone. Participants will be asked for verbal consent before starting the interview, which will be recorded for later transcription verbatim. Interviews will be semi-structured covering five main topic areas: preparation before the pandemic; intellectual, physical and emotional challenges during the pandemic; and learning for future events.

Follow-up feasibility

The consent rate will be collected, calculating the number of patients who agreed to participate divided by the number of patients who meet selection criteria, expecting a consent rate of > 70%. [39] The feasibility over-time during the follow-up will be measured as cohort retention rate, considering the number of patients who can be contacted and evaluated at 3 and 6 months. [40,41] The reasons for the lack of assessments will be recorded individually.

Sample size calculation

All patients meeting the eligibility criteria discharged from ICU between October 2020 and April 2021 (due to funding constraints) will be invited to participate.

Based on bed capacity and patient flow from previous years, we estimated that 20 to 30 mechanically ventilated adult patients are discharged monthly from each centre. This means the sampling universe ranges from 840 to 1260 patients.

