Hodgson et al (2017) found that a quarter of ICU survivors had severe or moderate disability at 6 months after discharge, and half of them had mild disability.[8] There is no information to estimate how much the prevalence of disability increases during a pandemic; however, the prevalence of mental health issues could be used as a proxy of the expected impact on physical health. Hodgson et al (2017) found that 22% of patients had anxiety or depressive symptoms at 6 months after discharge. Lee et al (2007) found that among survivors of the SARS outbreak, 40% had at least moderate anxiety one year after.[42] This is equivalent to a relative risk of 1.81. Considering that measurement time points are different, we have estimated our sample size assuming a relative risk (RR) of 1.5 or 1.6, which is more conservative than the estimation based on the literature. The different scenarios used for the sample size calculation appear in **Table 3**.

Table 3. Different plausible scenarios for sample size calculation

Outcome	Risk in non-pandemic situation	Risk during the pandemic	Type 1 error	Power	Sample size
WHODAS 2.0	25% severe or moderate disability	40% severe or moderate disability (RR=1.6)	0.05	0.8	343

WHODAS 2.0	40% some degree of disability	64% some degree of disability (RR=1.6)	0.05	0.8	288
WHODAS 2.0	50% mild disability	75% mild disability (RR=1.5)	0.05	0.8	388
HADS	22% anxiety or depressive symptoms	40% moderate anxiety (RR=1.8)	0.05	0.8	226

HADS, Hospital Anxiety and Depression Scale; WHODAS, World Health Organization Disability Assessment Schedule; RR, relative risk

The most plausible scenario is that 40% of ICU survivors discharged in a low demand period will have some degree of disability and this will increase to 64% for those discharged during high-demand periods. Considering loss to follow-up, we estimate 550 patients need to be recruited at ICU discharge; so 413 patients are assessed at 3 months after discharge (25% loss to follow-up) and 289 patients at 6 months (30% lost to follow-up).

Quantitative analysis

Categorical variables will be presented as absolute and relative frequencies for each subgroup (i.e. admission diagnosis and treatment centre) and time point (i.e. ICU discharge, 3 and 6 months follow-up). In the case of normally distributed continuous variables, these will be summarised using the mean and standard deviation, while for those non-normally distributed, the median and interquartile range will be used instead.

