The trajectory for each outcome measure will be estimated using longitudinal multilevel regression with robust standard errors to account for data coming from

seven treatment centres. If data have a normal distribution, a linear regression model will be chosen. In the case of right skewed data, a Poisson regression will be used. For HADS, IES-R and WHODAS 2.0, data will be analysed as total scores and categories given by each questionnaire.

Survival will be analysed using Kaplan-Meier curves. If the assumption of proportional hazards is met, survival will be compared between patients admitted due to COVID-19 vs. other causes using Cox regression. All analyses will be performed in Stata 16.0 SE.

Qualitative analysis

Data from the interviews with family members and critical care staff will be analysed using framework analysis.[43] Transcription will be aided by the software Scrintal and analysis by Nvivo 12.0. Two coders will listen and read in-full all interviews before meeting to explore potential common topics that were discussed during the interviews. These topics will form the initial coding framework. Through an iterative process these codes will be refined into overarching themes capturing differences and similarities across subgroups. A more advanced coding framework will be reviewed with members of the research team until agreement regarding the final framework is reached.

Themes will be used to explain the experience of family members during the pandemic and, potentially, identify areas where improvements could be made in the future. In the case of critical care staff, the aim is to explore to what extent the approach to the pandemic of each centre influenced the experience of the different clinical groups, and what can be learned for future outbreaks.

Findings will be shared with our participants and with other family members/ critical care staff that did not participate in the interviews to ensure our interpretation reflects their experiences.

Patient and public involvement

Patients or the public were not involved in the design, conduct, reporting, or dissemination plans of this study.

ETHICS AND DISSEMINATION

Ethical considerations

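### Robust standard errors are meant to handle seven centres, but cluster unit and reference distribution are unstated; clustering on centre with normal reference values would reject about 10% of the time at a nominal 5%

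*Combined protocol and SAP*

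**What the plan says.** The Quantitative analysis section estimates the trajectory of every outcome by "longitudinal multilevel regression with robust standard errors to account for data coming from" the seven treatment centres. The model is linear for normally distributed data; otherwise "In the case of right skewed data, a Poisson regression will be used". The software is named, but no variance option, degrees-of-freedom method or small-sample correction is given, and the random-effect levels are not listed. No other section supplies them.

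Study design and setting fixes the number of centres: "Participating sites are four public and three private hospitals". On size, Sample size calculation says only that "20 to 30 mechanically ventilated adult patients are discharged monthly from each centre".

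The contrasts at stake appear in three places. The primary objective in the Introduction is to "compare the trajectory of mental, physical and cognitive impairments at ICU discharge, 3 and 6 months" between patients admitted with COVID-19 and patients admitted for other causes. Under Measurement Outcomes, "The primary outcome measure is disability assessed at 6 months after ICU discharge" by WHODAS 2.0. The sample size instead rests on demand period: "The most plausible scenario is that 40% of ICU survivors discharged in a low demand period will have some degree of disability", against 64% in high-demand periods. A type 1 error of 0.05 appears in Table 3 and nowhere in the analysis section.

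**The concern.** The sentence gives the robust errors a job, which is to deal with the centres. Errors clustered on patient would not do that, so the direct way to carry out the sentence is to cluster on centre. A variance estimated from seven clusters carries at most about 6 degrees of freedom. Referring the resulting statistic to a normal distribution treats that variance as known and gives p-values that are too small and intervals that are too short.

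The sentence can also be read with a centre level in the multilevel model doing the work, and then the problem largely disappears under a common exposure effect. Two analysts who both follow the plan could therefore report intervals from the same data whose true coverage is about 95% in one case and about 90% in the other. The wording covers the primary WHODAS 2.0 outcome and every other outcome analysed this way.

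**Working it through.** The plan states no error rate or critical value for this test, so there is no figure of its own to reproduce.

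**Inputs from the documents**
- Centres: G = 7, so G − 1 = 6 (Study design and setting).
- Alpha: 0.05 (Table 3). Sidedness is not stated; two-sided is assumed.
- Patients at 6 months: 550 × 0.75 × 0.70 = 288.75, stated as 289 (Sample size calculation). The abstract gives a sample of 450, which at the same attrition leaves about 236. The exact result in step 1 does not use this number.
- Spread in centre throughput: 30/20 = 1.5 to 1 (Sample size calculation).

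**Assumed inputs (simulation only)**
- Intraclass correlation 0.02 and 0.05.
- Centre sizes 33 to 49, about 1.5 to 1.
- COVID-19 share 30 to 80% by centre, or a 50% high-demand share in every centre (the latter at intraclass correlation 0.05 only).
- Exposure effect either common to all centres or varying between them with SD 0.15 patient SD.

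**Step 1: exact balanced case.** With equal centres and the same exposure share in each, the estimate is the mean of seven centre-specific differences. The centre-clustered variance with the factor G/(G − 1) is then the usual variance of a mean of seven, so under normality the Wald statistic is t on 6 df. Size with normal reference values is 2P(t₆ > 1.960) = 9.8%. Without the factor it is 2P(t₆ > 1.960 × √(6/7)) = 12.0%.

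**Step 2: interval width.** The t(6) critical value is 2.447. 1.960/2.447 = 0.80, so normal-based intervals are about 20% too narrow. Conversely 2.447/1.960 = 1.25, so corrected intervals are about 25% wider.

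**Step 3: simulation under the null.** 289 patients, one 6-month record each, random-intercept generalised least squares, about 6,300 to 6,400 runs per setting (Monte Carlo SE 0.3 to 0.4 points). Rejection at nominal 5%, near-equal centres:

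| Centre-clustered inference | COVID-19 contrast | Demand contrast |
|---|---|---|
| Normal reference | 10.4–10.8% | 9.5–10.0% |
| t on 6 df | 5.2–5.6% | 5.0–5.2% |
| Bias-reduced variance, Satterthwaite df | 4.9–5.3% | 4.9–5.2% |
| Wild cluster bootstrap | 4.8% | 4.7–4.9% |

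A separate check with 50 centres and normal reference values gave 6.7%, so the excess comes mainly from having few clusters.

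**Step 4: the other reading.** With a common exposure effect, a random centre intercept with model-based errors gave 5.4 to 5.8%, and centre indicators with patient-level robust errors gave 5.3 to 5.7%. With the assumed SD of 0.15 between centres these became 7.9 to 9.4% and 7.8 to 9.1%.

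**Step 5: sensitivity to centre size.** With assumed sizes of 12 to 90, a spread of 7.5 to 1, centre clustering with normal reference values gave 12.0 to 13.4%, and t on 6 df gave 6.4 to 7.8%.

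**Step 6: log-link contrast.** A single Poisson contrast with centre-clustered variance and working independence, near-equal centres, gave 9.8% for a 40% binary outcome and 10.6% for a skewed score under normal reference values. With t on 6 df these were 5.0% and 5.7%. This is not the full multilevel Poisson model.

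**Step 7: power.** A contrast with 80% power under normal reference values has noncentrality 1.960 + 0.842 = 2.80. Referred to t on 6 df, its power is about 65%.

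**The case against.** The strongest reply is that the 10% needs two things the plan does not state: clustering on centre and a normal reference. The phrase about accounting for centres can be attached to the whole method, including the word multilevel. If a centre level carries the structure and the effect is common, the rate is 5 to 6% and little is wrong. This stands as a limit: the 10% is conditional and is not a prediction of what the analysts will do. It does not remove the point, because centre clustering is the most direct way to follow the sentence and nothing in the plan rules out normal reference values.

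A second reply is that the simulation is simpler than the planned analysis. It uses one record per patient, whereas the plan is longitudinal over three visits. That stands. A reader might infer that the 10% carries over to a group-by-time test or to the full multilevel Poisson model; neither was evaluated.

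A third reply concerns the higher figures. A reader might infer that rates of 12% or more are to be expected. The documents do not support this: their only indication of centre size is a 1.5 to 1 spread in monthly discharges, and the 7.5 to 1 spread is an assumption. Likewise, the 7.8 to 9.4% for varying effects depends on an assumed SD, and it counts as error only if the target is the mean effect over a wider population of centres, which the documents do not define.

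Finally, this is an observational cohort whose analysis section sets no alpha. But the study states a directional hypothesis and a primary outcome and is sized at 0.05 with 80% power, and interval coverage matters in a cohort as well.

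**Conclusion.** Wrong as written, on the centre-clustered reading. With normal reference values and centres of similar size, a single 6-month contrast rejects about 10% of the time at a nominal 5% (exact 9.8%), and 95% intervals are about 20% too narrow and cover about 90%. Marked inequality in centre size, which the documents do not indicate, would raise the rate to roughly 12% or more. On the alternative reading, with a common exposure effect, the rate is about 5 to 6%.

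The exact figure rests on the seven centres, the balanced case and the G/(G − 1) factor. The simulated figures also rest on the assumed correlation, exposure shares and centre sizes. A reader might conclude that the study's primary comparison will have a doubled error rate; the documents do not show that, because they fix neither the cluster unit nor the reference distribution.

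**What to change.** Amend the Quantitative analysis section to commit to one of two approaches.

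(a) Cluster on centre and replace normal reference values with t on 6 df as a minimum. Preferably use a bias-reduced cluster variance with Satterthwaite degrees of freedom, or a wild cluster bootstrap. Whether the planned software offers these for the multilevel linear and Poisson models is not shown in the documents and must be checked. Apply the same small-sample principle to any joint test.

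(b) Enter centre as indicators, cluster errors on patient, and state that a common exposure effect across the seven centres is assumed.

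Either is a sentence or two and needs no new data. Under (a), intervals are about 25% wider on 6 df, and a contrast with 80% power under normal reference values has about 65%. Part of that apparent power came from the excess rejection rate. Option (b) avoids this loss but depends on the common-effect assumption, so the plan should say why that assumption is acceptable.

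### The observed shape of each score decides between linear and Poisson regression, so the data choose whether recovery is compared in points or as a ratio

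*Combined protocol and SAP*

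**What the plan says.** The Introduction sets the aim: "The primary objective of this study is to compare the trajectory of mental, physical and cognitive impairments at ICU discharge, 3 and 6 months", between patients admitted for severe COVID-19 and those admitted for other causes. It also expects the groups to differ in level: "impairments will be higher in patients treated in periods of higher bed occupancy and those who had severe COVID-19".

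Under Quantitative analysis, "The trajectory for each outcome measure will be estimated using longitudinal multilevel regression with robust standard errors". The choice of model then depends on the data: "If data have a normal distribution, a linear regression model will be chosen", and "In the case of right skewed data, a Poisson regression will be used". The same paragraph adds: "For HADS, IES-R and WHODAS 2.0, data will be analysed as total scores and categories given by each questionnaire".

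The plan does not say:
- how normality or skew is judged, on scores or residuals, or at which visit;
- what happens to left-skewed scores;
- which link function or effect scale applies;
- whether Poisson results would be turned back into differences in points.

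Separately, Measurement Outcomes names WHODAS 2.0 disability at 6 months as the primary outcome measure.

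**The concern.** Comparing trajectories means asking whether change over time differs between groups. With an identity link, the quantity tested is the difference between two falls in points. With a log link, it is the ratio of two proportional changes. If the groups start level, the two null hypotheses coincide. If they start apart and scores change, equality on one scale implies inequality on the other.

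The rule therefore does more than pick a convenient error distribution. It lets the histogram of each instrument, seen after data collection, settle which question is asked of that instrument. Robust standard errors protect the variance estimate, but they do not restore a fixed target. At stake is whether a finding that COVID-19 patients recover differently, or do not, reflects the patients or the scale that the rule happened to select.

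**Working it through.** The plan states no figure for this contrast, so there is none to reproduce.

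**Inputs.** From Sample size calculation: 289 patients expected at 6 months (413 × 0.70 = 289). Assumed, because the documents give no values: a 1:1 split (144 per group), coefficient of variation CV = 0.6 at each visit, within-patient correlation ρ = 0.5, complete data, no centre effects, and all group means. Subscripts 0 and 1 mark ICU discharge and 6 months.

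**Step 1: when direction reverses.** Let group A start k times higher than group B, with proportional falls fA and fB. A falls more in points if k·fA > fB, and B falls more as a ratio if fB > fA. Both hold when fB/k < fA < fB. As an illustration only, take k from the planning ratios ("assuming a relative risk (RR) of 1.5 or 1.6", which are prevalence ratios, not ratios of mean scores) with fB = 50%:
- k = 1.6: fA between 0.50/1.6 = 31% and 50%.
- k = 1.5: fA between 0.50/1.5 = 33% and 50%.

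Example: A goes from 40 to 20 and B from 30 to 12. In points, A falls more (20 against 18). As a ratio, B falls more (to 40% of its start, against 50%).

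**Step 2: rejection rates by large-sample formula.**
- Points: D = (A0 − A1) − (B0 − B1). Each group contributes variance CV²(m0² + m1² − 2ρ·m0·m1)/n.
- Ratio: L = ln[(A1/A0)/(B1/B0)]. Its standard error is √[2 × CV² × (2 − 2ρ)/n] = √(2 × 0.36 × 1/144) = 0.0707.
- Two-sided 5% rejection probability: Φ(|z| − 1.96) + Φ(−|z| − 1.96).

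Worked case, both groups falling 20 points (45 to 25, 35 to 15): D = 0, so the linear test rejects 5%. L = ln(0.5556/0.4286) = 0.2595, z = 0.2595/0.0707 = 3.67, so the Poisson test rejects 96%.

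Worked case, both groups halving (44 to 22, 30 to 15): D = 22 − 15 = 7. The variances are 0.36 × 1452/144 = 3.63 and 0.36 × 675/144 = 1.69, so SE = √5.32 = 2.31, z = 3.04, and the linear test rejects 86%. L = 0, so the Poisson test rejects 5%.

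| Assumed means | Baseline gap | Linear, formula | Poisson, formula | Simulation |
|---|---|---|---|---|
| Equal 20-point falls: 40 to 20, 38 to 18 | 2 | 5% | 12% | Poisson 12–13% |
| Equal 20-point falls: 40 to 20, 36 to 16 | 4 | 5% | 38% | Poisson 38–39% |
| Equal 20-point falls: 45 to 25, 35 to 15 | 10 | 5% | 96% | linear 4–7%, Poisson 94–98% |
| Both halve: 40 to 20, 36 to 18 | 4 | 14% | 5% | linear 14–18% |
| Both halve: 44 to 22, 30 to 15 | 14 | 86% | 5% | linear 82–84%, Poisson 5–6% |
| Reversal: 40 to 20, 30 to 12 | 10 | 15% | 88% | linear 16%, Poisson 88% |

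The simulations drew right-skewed gamma scores and fitted linear and Poisson group-by-time models with patient-clustered robust errors. They agree closely with the formula.

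**Step 3: how often the two models contradict each other outright.** For 40 to 20 against 30 to 12, the two interaction estimates had opposite signs in 80% of runs, but both were significant in opposite directions in only 7–8%. A second example (40 to 24 against 20 to 10, with a different skewed distribution capped at 100) gave 9%, and a third (30 to 20 against 15 to 8) gave 1%.

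**Step 4: a single visit.** For positive means, A1 − B1 > 0 exactly when A1/B1 > 1. At one visit the two scales cannot disagree on direction.

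**The case against.** The rule is stated in advance and depends on distribution, not on the group effect or a p-value. That stands: this is not selection on significance. It does not answer the point, because the quantity tested still changes with the branch taken.

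The 94–98% and 82–84% figures need baseline gaps of 10 and 14 points, which nothing in the documents supports or excludes. That stands in full. At gaps of 2 to 4 points the effect is modest.

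The calculation is not the planned model. The plan uses multilevel regression with robust errors to handle seven centres, and the calculation has no centres. That limits the rejection rates. It does not touch Step 1, which concerns means alone.

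A reader might infer more than the documents support:
- *That Poisson is invalid because the scores are not counts.* With robust errors it estimates a ratio of means for any non-negative outcome.
- *That a score symmetric at one visit and skewed at another has no model.* The text chooses a model per outcome, not per visit. The rule is vague there, not empty.
- *That mixed scales prevent one combined statement across instruments.* No pooling is planned, and points on different instruments would not combine either.

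**Conclusion.** The concern holds for group-by-time contrasts on total scores, which is how the primary objective is framed. As written, the observed distribution decides which null hypothesis is tested, in groups the protocol expects to differ in level. Discordant significance is common when the baseline gap is large and modest when it is small. Significant findings in opposite directions are uncommon, about 7–9% in two examples chosen to reverse and 1% in a third. All these rates rest on the assumed means, CV, correlation, equal split and absence of centres.

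It would be wrong to conclude that the primary outcome could change direction. The between-group comparison of WHODAS 2.0 at 6 months is a single-visit comparison, so only the size and units of the effect depend on the branch. The category analyses and the sample size, which is built on proportions, are also outside the problem, but they do not settle the scale for total scores. This should be corrected before analysis. It does not put the study's design in doubt.

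**What to change.** Delete the distribution-based switch and name one effect scale in advance for the trajectory contrast of every score:
- Report the mean difference at each visit and the difference in change in points, from an identity-link mixed model with robust standard errors. If a log-link model is kept for any score, report the same quantities as marginal mean differences.
- State the group-by-time term explicitly.
- Present a ratio-scale analysis only as a labelled sensitivity analysis.
- Keep Poisson with robust errors for yes/no categories, where it gives the risk ratio used in the sample size section. Categories with more than two levels need a pre-stated cut-point or their own model.

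This costs SAP wording only, with no new data or patients. The downside is some loss of efficiency for very skewed scores. The change does not settle how robust errors should be computed with only seven centres, which needs its own statement.
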